7.7.2 Exploratory Efficacy Analyses

- 1) Change from baseline score in [REDACTED] along with the visit score will be summarized descriptively with 95% confidence interval for each of the 4 cohorts. Where applicable, both total and domain scores will be summarized. This summary will be performed for all visits scheduled for assessments.
- 2) A cumulative distribution function (CDF) plot will be created by cohort for percent of patients who experience a maximum of no improvement, 1-point improvement, 2-point improvement, up to 30-point improvement in [REDACTED] total score. A table summarizing number and percent of patients will also be presented.
- 3) CSU subjects achieving [REDACTED] will be tabulated with % of subjects for each study week. Similarly, subjects achieving [REDACTED] ≤ 6 and subjects achieving ≥ 10 point decrease from baseline will be tabulated for each week.
- 4) CSU subjects achieving ≥ 5 point decrease from baseline in [REDACTED] and [REDACTED] will be tabulated with % of subjects for each study week.

- 5) Change from baseline in [REDACTED] subjects will be summarized descriptively at each week.
- 6) The daily [REDACTED] will be summarized for each subject at each week. The weekly average scores will be listed for all subjects.
- 7) Changes in [REDACTED] and [REDACTED] will be summarized at each study visit.

7.8 Pharmacodynamic Analysis

Eosinophil count from peripheral blood collected pre-dosing will be summarized by visit.

7.9 Pharmacokinetic Analysis

AK002 blood concentration will be summarized by the visit the samples are collected.

7.10 Safety Analyses

7.10.1 Adverse Events

Safety assessments will be based mainly on the nature, frequency, relationship, and severity of adverse events (AEs). AEs will be coded by primary system organ class (SOC) and preferred term (PT) according to the Medical Dictionary for Regulatory Activities (MedDRA) version 21.0. The treatment-emergent adverse events (TEAEs) will be summarized by the number and percentage (n and %) of subjects in each SOC and PT. For summaries by relationship to study drug, “possibly related” will be combined with “related”, and “unlikely/remote related” will be combined with “not related.” When multiple AEs are reported with the same preferred term, the AE of the strongest relation will be included in the summary by relationship, and the AE of the most severe grade will be included in the summary by severity table.

The following AE incidence tables will be presented.

- Overview of TEAEs to include
 - Number (%) of subjects who reported at least one TEAE
 - Number (%) of subjects who reported at least one treatment-related TEAE
 - Number (%) of subjects who reported at least one severe TEAE
 - Number (%) of subjects who reported at least one serious TEAE
 - Number (%) of subjects who reported at least one TEAE leading to treatment discontinuation
- TEAEs by PT sorted by decreasing order of subject incidence in the combined cohort
- TEAEs by SOC and PT sorted alphabetically
- Study Drug-Related TEAEs by SOC and PT
- TEAEs Grade 2+ Severity by SOC and PT

- TESAEs by SOC and PT
- TEAEs leading to study drug discontinuation by SOC and PT

Select TEAEs of pain, tenderness, erythema/redness, induration/swelling, nausea/vomiting, diarrhea, headache, fatigue, and myalgia will be summarized with n and % by toxicity grade.

All AEs will be listed with onset/stop day, relationship to study drug, severity, action taken, and outcome. Pertinent subject information including cohort and demographics will also be included. Separate listings will be provided for TEAEs leading to study discontinuation and Treatment-emergent serious AEs (TESAEs).

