3.1 General Description

This is an open-label, pilot study to assess the efficacy and safety of AK002 in subjects with antihistamine-resistant chronic urticaria. The study comprises a screening period of 4 weeks, with daily oral intake of standard-dose (once daily) second-generation antihistamine (AH) (standard of care, with on-demand intake of up to 3 additional AH tablets per day). The treatment period comprises a daily oral intake of standard-dose second-generation AH and AK002 administered by IV infusion at Days 1, 29, 57, 85, 113, and 141. The primary and secondary endpoints will be evaluated at Week 10, 2 weeks after last dose, for subjects enrolled under Protocol Amendment 2.1 and Week 22, 2 weeks after last dose, for all remaining subjects (i.e., those on study during Protocol Amendment 3), and then patients will be followed for an additional 4 weeks (Week 24). The study design is presented schematically in [Table 1](#).

Table 1 Schedule of Assessments for the Main Study

Description	Visit 1	Visit 2	Visit 3	Visit 4	Visits 5, 6, 7	Visit 8	Visit 9	Visit 10
	Day -28	Day 1	Day 29 (± 2)	Day 57 (± 2)	Days 85, 113, and 141 (± 2)	Day 155 (± 2)	Day 169 (± 2)	Day 197 (± 2)
	Week -4	Week 0	Week 4	Week 8	Weeks 12, 16, and 20	Week 22	Week 24	Week 28
	Screening	Baseline/Dosing	Dosing	Dosing	Dosing ^r	Response Assessment ^t	Response Assessment	End of Study/ Early Term.
Informed consent	x ^a							
Eligibility assessment/ confirmation	x	x ^b						
Demographic data	x							
Medical history	x							
Prior CU treatment	x							
Prior/concomitant medication	x	x	x	x	x	x	x	x
Rescue medication use		x	x	x	x	x	x	x
Study Drug administration ^c		x	x	x	x			
Patient diary ^{d,s}	x	x	x	x	x	x	x	x
UAS7		x	x	x	x	x	x	x
		x	x	x	x	x	x	x
		x	x	x	x	x	x	x
UCT		x	x	x	x	x	x	x
q	x	x	x	x	x	x	x	x
		x	x	x	x	x	x	x
		x	x	x	x	x	x	x
		x	x	x	x	x	x	x
and FricTest® ^e	x (if applicable)	x (if applicable)	x (if applicable)	x (if applicable)				
Skin biopsy ^p		x				x		

Table 1 Scheduled of Assessments (continued)

Description	Visit 1	Visit 2	Visit 3	Visit 4	Visits 5, 6, 7	Visit 8	Visit 9	Visit 10
	Day -28	Day 1	Day 29 (± 2)	Day 57 (± 2)	Days 85, 113, and 141 (± 2)	Day 155 (± 2)	Day 169 (± 2)	Day 197 (± 2)
	Week -4	Week 0	Week 4	Week 8	Weeks 12, 16, and 20	Week 22	Week 24	Week 28
	Screening	Baseline/Dosing	Dosing	Dosing	Dosing ^r	Response Assessment ^t	Response Assessment	End of Study/ Early Term.
Anti-drug antibodies ^f		x	x		x	x		x
PK analysis ^f		x	x		x	x		x
Blood safety ^g	x	x	x	x	x	x	x	x

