3.5 Hypotheses

There are no formal tests of hypotheses in this study.

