3.6 Determination of Sample Size

The planned sample size of approximately 48 subjects is based on common practice in early phase, proof-of-concept studies.

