6.1 General Methodology

All statistical analyses will be conducted using SAS Version 9.4 or later on the Microsoft® Windows Operating System.

Continuous data will be summarized using n (number of subjects with non-missing observations), mean, median, standard deviation (SD), minimum value, and maximum value. Categorical data will be summarized using the frequency count and percentage (n, %) of subjects in each category. Number of subjects with non-missing values and number of subjects with missing values (e.g., Not Done) will be presented, where appropriate. Subjects with missing values will not contribute to the denominator of percentage calculations. Counts of zero in any category will be presented without percentage.

All endpoints will be summarized by the individual applicable cohorts (CholU, UF, CSU-XN or CSU-XF). Where appropriate, the summaries will also be carried out for all 4 cohorts combined.

Two-sided 95% confidence interval (CI) may be presented for the mean or percentage.

The precision rules for the presentation of summary statistics will be:

- Sample size (n, N) and number of missing responses (if displayed) – Integer
- Mean, CI – One more decimal place than reported/collected
- Standard deviation – Two more decimal places than reported/collected
- Median, other percentile, minimum, maximum – Same number of decimal places as reported/collected
- Ratio – two decimal places
- Percentage – one decimal place generally, or two decimal places for <0.1%

The data summaries will be accompanied by individual subject data listings. All data available from diary, questionnaires, eCRF, and external transfer (e.g., labs) will be listed and will include relevant and pertinent subject information, e.g. study day. The listings will be sorted in the order of Cohort and unique subject ID, and assessment name and assessment date/time.

Dates will be presented in the ISO-8601 format YYYY-MM-DD. Times will be displayed in 24-hour clock format. Numbering for tables, figures and listings will follow ICH E3 Guidelines ([ICH, 1996](#)).

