7.1.2 Safety Population

The safety population will consist of all subjects who signed informed consent, met all eligibility criteria at Screening, and having received at least one dose of study drug.

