7.7 Efficacy Analyses

7.7.1 Primary Efficacy Analysis

The primary efficacy variable is the change from baseline in UCT score for each population (CSU-XN, CSU-XF, UF, and CholU). UCT score and its change from baseline will be summarized using descriptive statistics by study visit (Weeks 4, 8, 10, 12, 16 for subjects enrolled under Protocol Amendment 2.1 and Weeks 4, 8, 12, 16, 20, 22, 24, and 28 for subjects enrolled after Protocol

Amendment 3). A 95% CI for the mean change will be computed. The summaries will be provided for each cohort.

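### TEAE tables pool a shorter and a longer treatment schedule; the crude percentages can understate six-infusion incidence and should also be shown by schedule

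*SAP*

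**What the plan says.** **Adverse-event tables.** SAP 7.10.1 states: "The treatment-emergent adverse events (TEAEs) will be summarized by the number and percentage (n and %) of subjects in each SOC and PT". The tables listed there are all subject counts with percentages, including "TEAEs by PT sorted by decreasing order of subject incidence in the combined cohort". SAP 6.1 sets the columns: "All endpoints will be summarized by the individual applicable cohorts (CholU, UF, CSU-XN or CSU-XF", with all four cohorts combined where appropriate. No table is split by schedule.

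**Denominator and window.** SAP 7.1.2 reads: "The safety population will consist of all subjects who signed informed consent, met all eligibility criteria at Screening, and having received at least one dose". The SAP's definitions table (Section 4) starts the treatment-emergent period at the first administration and gives it no end.

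**Two schedules.** SAP 3.1 has the endpoints "evaluated at Week 10, 2 weeks after last dose, for subjects enrolled under Protocol Amendment 2.1 and Week 22, 2 weeks after last dose" for the remaining subjects. SAP 7.7.1 lists the UCT visits as "Weeks 4, 8, 10, 12, 16 for subjects enrolled under Protocol Amendment 2.1 and Weeks 4, 8, 12, 16, 20, 22, 24, and 28", the second list being for those enrolled after Amendment 3. SAP 7.7.1.3 limits one count of UCT responses to Amendment 3 subjects. For the current schedule, protocol 11.6.1 records adverse events to Day 197 or early termination.

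**Related provisions.** SAP 7.6.1 tabulates subjects by number of doses received and summarises duration of exposure. SAP 7.10.1 also lists every event with its onset and stop day.

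**The concern.** A subject planned for half the infusions and observed for 16 of 28 weeks weighs as much in the TEAE denominator as a full-course subject. The pooled percentage then describes a mixture of two regimens. A reader looking for the adverse-event incidence of the current six-infusion regimen has no column that gives it.

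If underlying risk is the same in both groups of subjects, the mixing can only lower the six-infusion figure or leave it unchanged. It cannot raise it. If the mix also varies by cohort, cohort columns can differ for reasons unrelated to disease type.

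This matters because SAP 2.1 makes safety part of the primary objective, and protocol 13.8 describes the study as a first characterisation of effect, safety and tolerability.

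**Working it through.** **1. The plan's own durations.** SAP 3.2.2 gives about 32 weeks in total: 4 + 20 + 8 = 32, so 20 + 8 = 28 weeks follow the first dose. This matches Day 197 (Week 28) in the protocol's Table 1.

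**2. The shorter schedule (inferred).** The text of Amendment 2.1 is not among the documents.
- Last dose: Week 10 − 2 = Week 8.
- Infusions at the 28-day interval in protocol 6.1.2: 8/4 + 1 = 3. The same sum for later subjects gives (22 − 2)/4 + 1 = 6, which agrees with the stated dosing days.
- Observation: the last UCT visit is Week 16. The current protocol synopsis collects TEAEs until 8 weeks after the last dose, and 8 + 8 = 16 is consistent with that.

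Planned shortfall against the longer schedule: (28 − 16)/28 = 43% of the window and 3/6 = 50% of the infusions. These are differences in exposure, not bias in any reported percentage.

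**3. Dilution model.** Let p be the true incidence over the six-infusion schedule, q the incidence seen on the shorter one, and f the share of subjects on the shorter one.
- Pooled percentage = f·q + (1 − f)·p
- Constant hazard over time: q = 1 − (1 − p)^(16/28)
- Constant risk per infusion: q = 1 − (1 − p)^(3/6)
- Part of the risk, a, at the first infusion and constant hazard for the rest: q = 1 − (1 − a)·[(1 − p)/(1 − a)]^(16/28)

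The documents give neither p nor f, so both are assumed.

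| True p | Model | q | Pooled, f = 25% | Pooled, f = 50% |
|---|---|---|---|---|
| 10% | constant hazard | 5.8% | 9.0% | 7.9% |
| 30% | constant hazard | 18.4% | 27.1% | 24.2% |
| 50% | constant hazard | 32.7% | 45.7% | 41.4% |
| 70% | constant hazard | 49.7% | 64.9% | 59.9% |
| 50% | constant risk per infusion | 29.3% | 44.8% | 39.6% |
| 50% | 40 points at first infusion | 45.9% | 49.0% | 48.0% |
| 50% | all at first infusion | 50.0% | 50.0% | 50.0% |

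Worked example: 1 − 0.5^(16/28) = 0.327, and 0.25 × 0.327 + 0.75 × 0.50 = 0.457. At f = 75% under constant hazard the pooled figure is 37.0%, which is 13.0 points low.

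**4. Cohort columns.** Take 12 subjects per cohort, the same true 50% and a constant hazard.
- 0 of 12 against 6 of 12 on the shorter schedule: 50.0% against 41.4%, a gap of 8.6 points.
- 6 of 12 in both: no gap.

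**5. The longer window is itself unsettled.** SAP 5.6 has adverse-event reporting at Visits 2–7, and SAP 6.6 starts the analysis after Visit 7. Weeks −4, 0, 4, 8, 10, 12 and 16 make seven visits, so both fit the shorter schedule. In the current schedule Visit 7 is Day 141 (Week 20), the day of the sixth infusion, whereas protocol 5.2 runs safety reporting to Visit 10. If the six-infusion window did stop at Week 20, an incidence of 50% by then would give q = 1 − 0.5^(16/20) = 42.6%. The pooled figures would be 0.25 × 42.6 + 0.75 × 50 = 48.1% and 0.50 × 42.6 + 0.50 × 50 = 46.3%.

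**The case against.** **The size is unknown and may be small.** The number of Amendment 2.1 subjects is not given. SAP 5.1 assigns to Week 22 those on study during Amendment 3, while SAP 7.7.1 speaks of those enrolled after it, so some early subjects may have moved to the longer schedule. Infusion-related reactions are the drug reactions described in protocol 2.8; to the extent that they fall at the first infusion, pooling loses nothing. All of this stands. The effect can only be stated conditionally.

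**No cohort comparison is planned.** SAP 3.5: "There are no formal tests of hypotheses in this study". SAP 3.6: "The planned sample size of approximately 48 subjects is based on common practice in early phase, proof-of-concept studies". A gap of 8.6 points is about one subject in 12 (8.3 points), and the exact 95% interval for 6/12 runs from 21% to 79%. This stands for the cohort columns. It is weaker for the combined column, which has about 48 subjects. Imprecision is also no reason to leave in a mixture that can be separated.

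**The mix will be visible.** SAP 7.6.1 shows dose counts and the listings show event days. That is partial handling: a reader could rebuild the split by hand, but no planned table links exposure to the event percentages.

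**Exposure adjustment has its own bias.** Suppose all risk falls at the first infusion and is 50% on both schedules. Event-free subjects then contribute 16 or 28 weeks, and the rates are 0.5/(0.5 × 16) = 6.25 and 0.5/(0.5 × 28) = 3.57 per 100 person-weeks. That is a spurious 1.75-fold excess where the crude percentages are right. Truncating everyone at Week 16 does not equalise exposure either, because later subjects are infused again at Weeks 12 and 16. This stands and limits the remedy.

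**A stronger reading is tempting.** A reader might infer that the six-infusion incidence is definitely understated and that the cohort columns are not comparable. The documents support neither as fact. The first needs three-infusion subjects in the pool and risk that continues after their window closes. The second needs unequal shares across cohorts. Nor does the SAP label the pooled percentage as the six-infusion rate.

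**Conclusion.** The point holds in conditional form. The TEAE tables pool two planned schedules in one crude percentage, although the SAP separates the same schedules for efficacy. The pooled figure can understate six-infusion incidence for events that continue after the third infusion or Week 16.

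For a true incidence of 50%, the understatement runs from zero (all risk at the first infusion) to 13 points (constant hazard, 75% on the shorter schedule). At shares of 25% or 50% under constant hazard it is 4.3 or 8.6 points. Constant risk per infusion gives somewhat larger values, 5.2 or 10.4 points at the same shares. All of these rest on assumed shares and incidences, on the inferred 3 infusions and 16 weeks, and on a six-infusion window that reaches Week 28. They ignore any effect of dose level.

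Distortion between cohort columns is possible but cannot be shown from the documents. This is an inexpensive improvement to safety reporting. It does not invalidate the planned tables.

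**What to change.** In SAP 7.10.1, keep the crude tables and add the following.
- TEAE n (%) in separate columns for the 3-infusion and 6-infusion schedules, at least in the overview, SOC/PT and drug-related tables.
- Classification by the schedule the subject actually followed, so that anyone moved to the longer schedule counts there. It should not be by doses received: a subject who stops early because of an event must stay with the schedule they were on.
- The number of subjects on each schedule in each cohort.
- A statement that the 6-infusion column is the one to cite for the current regimen.

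Exposure-adjusted rates may be added as a supplement with the constant-rate assumption stated. They should not be the basis for comparing cohorts.

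Separately, reconcile the adverse-event window in SAP 5.6 (Visits 2–7) with Day 197 in protocol 11.6.1, check SAP 6.6 against the same schedule, and settle the wording in SAP 5.1 and 7.7.1 on who belongs to which schedule.

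The cost is SAP wording and a few table columns from data already collected. The downside is smaller denominators in the split columns, which will be very small within a cohort of about 12.

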7.10.2 Laboratory Test

Laboratory data will be summarized by presenting summary statistics of raw data and change from baseline values (means, medians, standard deviations, ranges) at each visit for sample collection. For quantitative laboratory parameters, both actual values and change from baseline values will be summarized.

Shift tables will be presented, in which, lab test results at baseline and post-baseline will be classified into below (<LLN), within (\geq LLN and \leq ULN), and above ($>$ ULN) normal ranges. Subject incidences (n and %) will be presented for the shift from baseline to the post-baseline visits.

Note the summary and shift tables will only use the planned/scheduled tests. However, both scheduled and unscheduled/repeat tests will be included in the data listing.

A complete laboratory data listing, including hematology, biochemistry, urinalysis, and anti-drug antibodies will be provided for all subjects.

7.10.3 ECG

The investigator overall evaluation of normal, abnormal not clinically significant, and abnormal clinically significant ECG findings will be tabulated with number and % of subjects for each assessment visit.

Actual and change from baseline in PR, QRS, QT, RR, QTc, and HR will be summarized with descriptive statistics for each assessment visit.

Data listings will be presented for ECG parameters by visit. QTc meeting the criteria of >450 but ≤ 480 , >480 but ≤ 500 or >500 msec for the actual value, or >30 msec or >60 msec increase from baseline will be identified.

7.10.4 Vital Signs and other safety measures

Vital signs will be summarized by presenting summary statistics of raw data and change from baseline values (means, medians, standard deviations, ranges) for each scheduled visit and time point. A data listing will include vital signs from all visits.

Other safety assessments will be listed.

8. Analysis Plan for the Extension Part of the Study

The extension part of the study will have the same conduct and data collection as for the main part of the study. A few exceptions are that the extension part (1) enrolls only patients meeting entry criteria from certain sites, (2) provides patients longer and flexible treatment (see 3.23.2.1), (3) eliminates some data collections, e.g., QoL instruments (see Table 1 and Table 2). The analysis for the extension study will virtually be the same as for the main study with some adjustment for the visit schedules. No separate analysis plan will be developed for this part of the study.

9. Validation

The Clinical Operations, Data Management and Biostatistics groups at Allakos will work with EDC/Data Management (DM) vendor to ensure that the data collected for the study are of the highest quality possible. The study monitor will be responsible for reviewing and verifying the accuracy of the data recorded on the electronic case report forms (eCRFs) direct from source documents at the investigative site. The DM vendor will be responsible for performing edit checks and reviewing all data entered into the electronic database to identify discrepant and/or inconsistent values and to send queries to the clinical sites. The Investigator will be responsible for answering queries about discrepant data and providing electronic signatures to confirm data integrity.

The programming of Tables, Listings and Figures (TLFs) based on the clinical data is outsourced to Etera Solutions (Etera). Allakos seeks to ensure the quality of the reports provided by Etera in the form of TLFs passing a rigorous validation process involving the following processes:

- Derived datasets will be independently reprogrammed by a second programmer. The separate datasets produced by the 2 programmers must match 100%.
- Tables will be independently reprogrammed by a second programmer and the results from both programs must match.
- Figures will be checked for consistency against corresponding tables and listings, or independently reprogrammed if there are no corresponding tables or listings.
- Listings will be checked for consistency against corresponding tables, figures, and derived datasets.

The entire set of TLFs will be checked for completeness and consistency prior to its delivery to Allakos.

10. References

International Council for Harmonisation (ICH). Guideline for industry E3, structure and content of clinical study reports, July 1996.

11. Appendices

- 11.1 Appendix A: Exclusion Criteria for the Per Protocol Populations
- 11.2 Appendix B.1.1: Urticaria Patient Daily Diary for Patient with Cholinergic Urticaria
- 11.3 Appendix B.1.2: Urticaria Patient Daily Diary for Patient with Urticaria Factitia
- 11.4 Appendix B.1.3 Urticaria Patient Daily Diary for Patients with Chronic Spontaneous Urticaria
- 11.5 Appendix B.2: Urticaria Control Test
- 11.6 Appendix B.3 [REDACTED]
- 11.7 Appendix B.4: [REDACTED]
- 11.8 Appendix B.5: [REDACTED]
- 11.9 Appendix B.6: [REDACTED]
- 11.10 Appendix B.7: [REDACTED]
- 11.11 Appendix B.8: [REDACTED]
- 11.12 Appendix C: List of Tables, Listings, and Figures
- 11.13 Appendix D: Table and Listing Shells

